11. SUPPORTING DOCUMENTATION AND OPERATIONAL CONSIDERATIONS

Appendix A Actions required in cases of increases in liver biochemistry and evaluation of Hy's Law

A 1 Introduction

This Appendix describes the process to be followed in order to identify and appropriately report cases of Hy's Law. It is not intended to be a comprehensive guide to the management of elevated liver biochemistries.

During the course of the study the Investigator will remain vigilant for increases in liver biochemistry. The Investigator is responsible for determining whether a patient meets potential Hy's Law (PHL) criteria at any point during the study.

The Investigator participates, together with AstraZeneca clinical project representatives, in review and assessment of cases meeting PHL criteria to agree whether Hy's Law (HL) criteria are met. HL criteria are met if there is no alternative explanation for the elevations in liver biochemistry other than drug induced liver injury (DILI) caused by the investigational medicinal products (IP).

The Investigator is responsible for recording data pertaining to PHL/HL cases and for reporting Adverse Events (AE) and Serious Adverse Events (SAE) according to the outcome of the review and assessment in line with standard safety reporting processes.

A 2 Definitions

Potential Hy's Law (PHL)

Aspartate aminotransferase (AST) or alanine aminotransferase (ALT) $\geq 3 \times$ upper limit of normal (ULN) **together with** total bilirubin (TBL) $\geq 2 \times$ ULN at any point during the study following the start of study medication irrespective of an increase in alkaline phosphatase (ALP).

Hy's Law (HL)

AST or ALT $\geq 3 \times$ ULN **together with** TBL $\geq 2 \times$ ULN, where no other reason, other than the IMP, can be found to explain the combination of increases, eg, elevated ALP indicating cholestasis, viral hepatitis, another drug.

For PHL and HL the elevation in transaminases must precede or be coincident with (ie, on the same day) the elevation in TBL, but there is no specified time frame within which the elevations in transaminases and TBL must occur.

A 3 Identification of potential Hy's Law cases

In order to identify cases of PHL it is important to perform a comprehensive review of laboratory data for any patient who meets any of the following identification criteria in isolation or in combination:

- ALT $\geq 3 \times$ ULN

- AST $\geq 3 \times$ ULN
- TBL $\geq 2 \times$ ULN

When a patient meets any of the identification criteria, in isolation or in combination, the central laboratory will immediately send an alert to the Principal Investigator.

The Investigator will also remain vigilant for any local laboratory reports where the identification criteria are met without an alternative explanation, where this is the case the Investigator will:

- Notify the AstraZeneca representative
- Request a repeat of the test (new blood draw) by the central laboratory
- Complete the appropriate unscheduled laboratory CRF module(s) with the original local laboratory test result

When the identification criteria are met from central or local laboratory results the Investigator will without delay:

- Determine whether the patient meets PHL criteria (see Appendix A 2 for definition) by reviewing laboratory reports from all previous visits (including both central and local laboratory results)

The Investigator will without delay review each new laboratory report and if the identification criteria are met and there is no alternative explanation the investigator will:

- Notify the AstraZeneca representative
- Determine whether the patient meets PHL criteria (see Appendix A 2 for definition) by reviewing laboratory reports from all previous visits
- Promptly enter the laboratory data into the laboratory CRF

A 4 Follow-up

A 4.1 Potential Hy's Law criteria not met

If the patient does not meet PHL criteria the Investigator will:

- Inform the AstraZeneca representative that the patient has not met PHL criteria.
- Perform follow-up on subsequent laboratory results according to the guidance provided in the Clinical Study Protocol.

A 4.2 Potential Hy's Law criteria met

If the patient does meet PHL criteria the Investigator will:

Determine whether PHL criteria were met at any study visit prior to starting Study treatment
(See Section 8.4 Safety Reporting)

- Notify the AstraZeneca representative who will then inform the central Study Team

The Study Physician contacts the Investigator, to provide guidance, discuss and agree an approach for the study patients' follow-up and the continuous review of data. Subsequent to this contact the Investigator will:

- Monitor the patient until liver biochemistry parameters and appropriate clinical symptoms and signs return to normal or baseline levels, or as long as medically indicated
- Investigate the aetiology of the event and perform diagnostic investigations as discussed with the Study Physician.
- Complete the three Liver CRF Modules as information becomes available
- If at any time (in consultation with the Study Physician the PHL case meets serious criteria, report it as an SAE using standard reporting procedures.

A 5 Review and assessment of potential Hy's Law cases

The instructions in this section should be followed for all cases where PHL criteria are met.

No later than 3 weeks after the biochemistry abnormality was initially detected, the Study Physician contacts the Investigator in order to review available data and agree on whether there is an alternative explanation for meeting PHL criteria other than DILI caused by the IMP. The AstraZeneca Global Clinical Lead or equivalent and Global Safety Physician will also be involved in this review together with other patient matter experts as appropriate.

According to the outcome of the review and assessment, the Investigator will follow the instructions below.

If there is an agreed alternative explanation for the ALT or AST and TBL elevations, a determination of whether the alternative explanation is an AE will be made and subsequently whether the AE meets the criteria for a SAE:

- If the alternative explanation is **not** an AE, record the alternative explanation on the appropriate CRF
- If the alternative explanation is an AE/SAE, record the AE /SAE in the CRF accordingly and follow the AZ standard processes

If it is agreed that there is **no** explanation that would explain the ALT or AST and TBL elevations other than the IMP:

- Report an SAE (report term 'Hy's Law') according to AstraZeneca standard processes.

- The ‘Medically Important’ serious criterion should be used if no other serious criteria apply
- As there is no alternative explanation for the HL case, a causality assessment of ‘related’ should be assigned.

If there is an unavoidable delay of over 3 weeks in obtaining the information necessary to assess whether or not the case meets the criteria for HL, then it is assumed that there is no alternative explanation until such time as an informed decision can be made:

- Report an SAE (report term ‘Potential Hy’s Law’) applying serious criteria and causality assessment as per above
- Continue follow-up and review according to agreed plan. Once the necessary supplementary information is obtained, repeat the review and assessment to determine whether HL criteria are met. Update the SAE report according to the outcome of the review amending the reported term if an alternative explanation for the liver biochemistry elevations is determined.

A 6 Actions required when potential Hy’s Law criteria are met before and after starting study treatment

This section is applicable to patients liver metastases who meet PHL criteria on Study treatment having previously met PHL criteria at a study visit prior to starting Study treatment.

At the first on-study treatment occurrence of PHL criteria being met, the Investigator will determine if there has been a significant change in the patients’ condition compared with the last visit where PHL criteria were met.

- If there is no significant change, no action is required
- If there is a significant change, notify the AstraZeneca representative, who will inform the central Study Team, then follow the subsequent process described in Appendix B 5.
- A ‘significant’ change in the patient’s condition refers to a clinically relevant change in any of the individual liver biochemistry parameters (ALT, AST or total bilirubin) in isolation or in combination, or a clinically relevant change in associated symptoms. The determination of whether there has been a significant change will be at the discretion of the Investigator, this may be in consultation with the Study Physician if there is any uncertainty.

A 7 Actions required for repeat episodes of potential Hy’s Law

This section is applicable when a patient meets PHL criteria on study treatment, and has already met PHL criteria at a previous on study treatment visit.

The requirement to conduct follow-up, review, and assessment of a repeat occurrence(s) of PHL is based on the nature of the alternative cause identified for the previous occurrence.

The investigator should determine the cause for the previous occurrence of PHL criteria being met and answer the following question:

Was the alternative cause for the previous occurrence of PHL criteria being met found to be the disease under study (eg, chronic or progressing malignant disease, severe infection or liver disease), or did the subject meet PHL criteria prior to starting study treatment and at first on-study treatment visit, as described in Appendix A6.

If **No**: Follow the process described in Appendix A 4.1.

If **Yes**: Determine if there has been a significant change in the patient's condition compared with when PHL criteria were previously met.

If there is no significant change, no action is required.

If there is a significant change, follow the process described in Appendix A 4.

A 'significant' change in the patient's condition refers to a clinically relevant change in any of the individual liver biochemistry parameters (ALT, AST or total bilirubin) in isolation or in combination, or a clinically relevant change in associated symptoms. The determination of whether there has been a significant change will be at the discretion of the Investigator; this may be in consultation with the AstraZeneca Physician if there is any uncertainty.

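### Appendix A 7 routes some repeat potential Hy's Law cases to the process for patients who do not meet the criteria; A 6 has a lesser wrong cross-reference

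*Combined protocol and SAP*

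**What the plan says.** The combined protocol and SAP sets out the liver-signal procedure in Appendix A.

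- **A 7, scope:** "This section is applicable when a patient meets PHL criteria on study treatment, and has already met PHL criteria" at an earlier on-treatment visit. It adds: "The requirement to conduct follow-up, review, and assessment of a repeat occurrence(s) of PHL is based on the nature of the alternative cause" found for the earlier episode.
- **A 7, question:** it asks whether the earlier episode was explained by the disease under study, with malignant disease, severe infection and liver disease as examples, or whether the patient is an A 6 case (criteria already met before treatment).
- **A 7, 'No' branch:** "Follow the process described in Appendix A 4.1".
- **A 7, 'Yes' branch:** no action if the patient's condition has not changed significantly; otherwise "If there is a significant change, follow the process described in Appendix A 4".
- **A 4.1, entry condition:** "If the patient does not meet PHL criteria the Investigator will", followed by two actions: tell the company representative that the criteria were not met, and follow later laboratory results as usual.
- **A 4.2, entry condition:** "If the patient does meet PHL criteria the Investigator will", followed by the full follow-up process.
- **A 5:** its review and assessment apply to every case that meets PHL criteria.
- **A 6:** where there is a significant change, the investigator notifies the company and then follows Appendix B 5. In this document B5 describes what counts as an important medical event.

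**The concern.** Every patient handled under A 7 meets PHL criteria by definition, so the entry condition of A 4.1 is false for every patient whom the 'No' branch sends there. The first A 4.1 action would have the investigator make an untrue report about a liver signal.

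The group matters clinically. 'No' includes earlier episodes for which nothing other than the study drugs was found, so drug-induced injury is a live question when the signal returns. At stake are the A 4.2 steps that a site might miss or delay, above all "Investigate the aetiology of the event and perform diagnostic investigations as discussed with the Study Physician" and "Complete the three Liver CRF Modules as information becomes available". A 7 also presents itself as the specific rule for repeat episodes, so a site could reasonably follow it in preference to the general text of A 4.2 and A 5.

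**Working it through.** No arithmetic underlies the point beyond a count. The check follows each cross-reference to its target and compares the target's entry condition with the patients sent there.

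| Route | Patients sent | Target's condition | Result |
|---|---|---|---|
| A 7 'No' to A 4.1 | PHL met, again | PHL not met | Contradiction |
| A 7 'Yes' with significant change to A 4 | PHL met, again | Both cases, so A 4.2 applies | Consistent |
| A 6 with significant change to B 5 | PHL met before and on treatment | Definition of an important medical event | Wrong target |

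**What would be lost if A 4.2 were skipped.** A 4.2 contains six investigator steps and one Study Physician contact, 6 + 1 = 7 actions.

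| A 4.2 action | Cover elsewhere |
|---|---|
| Check for PHL before treatment | Partial: A 7's own question asks about it |
| Notify the company representative | Partial: A 3 requires it where there is no alternative explanation |
| Study Physician contact | Partial: A 5 requires contact within 3 weeks of detection |
| Monitor until values and symptoms settle | Partial: laboratory follow-up in A 4.1; adverse event follow-up in Section 8.3.3 |
| Investigate aetiology | Partial: A 5 provides for obtaining the information needed to decide on Hy's Law, continued follow-up to an agreed plan, and reassessment |
| Complete the three Liver CRF Modules | None: A 3 and A 5 call for other CRF entries only |
| Report as an SAE if serious | Covered: A 5 and Section 8.4.1 |

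Actions with at least partial cover: 7 − 1 = 6. The explicit order to perform diagnostic investigations still appears only in A 4.2, so the cover for that action is incomplete.

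**Who is affected.** To reach the 'No' branch, a patient must have a second PHL episode on treatment, after a first that was not put down to malignancy, severe infection or liver disease, and must not be an A 6 case. The documents give no PHL frequency, so no expected count can be calculated for the 30 patients.

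**The A 6 route.** Inclusion criterion 9 (Section 5.1) caps total bilirubin at 1.5 × ULN; PHL needs at least 2 × ULN (A 2). Since 1.5 < 2, a patient at the entry limit is below the bilirubin threshold for PHL, and pre-treatment PHL should be rare. A 6 also orders notification before the faulty pointer.

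**The case against.** The strongest reply is that the error exposes itself. An investigator who has just established that PHL criteria are met cannot truthfully report the opposite. A 4.2, with the matching condition, comes straight after A 4.1, and A 5 claims every PHL case. Other text points the same way:

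- The note in Section 8.2.1 and Section 8.3.8 send such cases to Appendix A as a whole.
- Section 8.2.1 asks for clinically significant abnormal results to be repeated promptly.
- Section 8 requires immediate discussion of safety concerns with the overall principal investigator.
- Sections 8.3.3 and 8.4.1 keep adverse event follow-up and SAE reporting in force.

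Most of this stands, and it is why the point is minor. It does not remove the contradiction: the site must choose between conflicting instructions, and the one written specifically for repeat episodes is the wrong one.

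Four stronger readings are tempting, and the documents do not support them:

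- **Follow-up of recurrent liver injury would be lost.** A 4.2 and A 5 apply on their own terms. If the information needed is delayed beyond 3 weeks, A 5 assumes no alternative explanation and requires an SAE report.
- **The aetiology work-up exists only in A 4.2.** The explicit instruction does, but A 5 gives partial cover.
- **'No' means any earlier episode not due to the cancer.** A 7 also places severe infection and liver disease under 'Yes'. Conversely, 'No' is not confined to suspected drug injury: an earlier episode explained by another drug would also fall there.
- **The 'No' group gets the lightest handling of all.** 'Yes' without significant change requires no action. The anomaly is relative to 'Yes' with significant change, which reaches A 4.2.

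**Conclusion.** The concern holds: A 7's 'No' branch is wrong as written, and minor. It sends patients who meet PHL criteria to a process whose condition they cannot satisfy, in conflict with A 4.2 and A 5. The practical exposure is confusion or delay rather than certain loss of follow-up, with only the three Liver CRF Modules lacking any cover elsewhere. That few if any of the 30 patients would be affected is a judgement from the narrow route into the branch, since the documents give no event rate. No endpoint definition, decision rule, sample size, error rate or response analysis changes.

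The A 6 pointer is also wrong but matters less. It may be a slip for A 5, though the document does not confirm that.

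**What to change.** In A 7, change the 'No' branch to refer to Appendix A 4.2, then A 5. In A 6, replace Appendix B 5 with the Appendix A process for PHL criteria met (A 4.2, A 5 or both). The A 6 target is inferred from content, so the sponsor should confirm it.

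The cost is two cross-references in the next amendment. No procedure is added beyond what A 4.2 and A 5 already require when PHL criteria are met.

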Appendix B Adverse event definitions and additional safety information

B1 Definition of adverse events

An adverse event is the development of any untoward medical occurrence in a patient or clinical study patient administered a medicinal product and which does not necessarily have a causal relationship with this treatment. An AE can therefore be any unfavourable and unintended sign (e.g. an abnormal laboratory finding), symptom (for example nausea, chest pain), or disease temporally associated with the use of a medicinal product, whether or not considered related to the medicinal product.

The term AE is used to include both serious and non-serious AEs and can include a deterioration of a pre-existing medical occurrence. An AE may occur at any time, including run-in or washout periods, even if no Study treatment has been administered.

B2 Definitions of serious adverse event

A serious adverse event is an AE occurring during any study phase (i.e., run-in, treatment, washout, follow-up), that fulfils one or more of the following criteria:

12. Results in death
13. Is immediately life-threatening
14. Requires in-patient hospitalisation or prolongation of existing hospitalisation
15. Results in persistent or significant disability or incapacity.
16. Is a congenital abnormality or birth defect
17. Is an important medical event that may jeopardise the patient or may require medical treatment to prevent one of the outcomes listed above.

B3 Life threatening

‘Life-threatening’ means that the patient was at immediate risk of death from the AE as it occurred or it is suspected that use or continued use of the product would result in the patient’s death. ‘Life-threatening’ does not mean that had an AE occurred in a more severe form it might have caused death (e.g., hepatitis that resolved without hepatic failure).

B4 Hospitalisation

Outpatient treatment in an emergency room is not in itself a serious AE, although the reasons for it may be (e.g., bronchospasm, laryngeal oedema). Hospital admissions and/or surgical operations planned before or during a study are not considered AEs if the illness or disease existed before the patient was enrolled in the study, provided that it did not deteriorate in an unexpected way during the study.

B5 Important medical event or medical treatment

Medical and scientific judgement should be exercised in deciding whether a case is serious in situations where important medical events may not be immediately life threatening or result in death, hospitalisation, disability or incapacity but may jeopardize the patient or may require medical treatment to prevent one or more outcomes listed in the definition of serious. These should usually be considered as serious.

Simply stopping the suspect drug does not mean that it is an important medical event; medical judgement must be used.

18. Angioedema not severe enough to require intubation but requiring iv hydrocortisone treatment
19. Hepatotoxicity caused by paracetamol (acetaminophen) overdose requiring treatment with N-acetylcysteine
20. Intensive treatment in an emergency room or at home for allergic bronchospasm
21. Blood dyscrasias (e.g., neutropenia or anaemia requiring blood transfusion, etc.) or convulsions that do not result in hospitalisation
22. Development of drug dependency or drug abuse

B6 Intensity rating scale:

The grading scales found in the revised National Cancer Institute CTCAE latest version (5.0) will be utilised for all events with an assigned CTCAE grading. For those events without assigned CTCAE grades, the recommendation in the CTCAE criteria that converts mild, moderate and severe events into CTCAE grades should be used. A copy of the CTCAE can be downloaded from the Cancer Therapy Evaluation Program website (<http://ctep.cancer.gov>). The applicable version of CTCAE should be described clearly.

For each episode of an adverse event, all changes to the CTCAE grade attained as well as the highest attained CTC grade should be reported.

It is important to distinguish between serious and severe AEs. Severity is a measure of intensity whereas seriousness is defined by the criteria in Appendix B2. An AE of severe intensity need not necessarily be considered serious. For example, nausea that persists for several hours may be considered severe nausea, but not a SAE unless it meets the criteria shown in Appendix B2. On the other hand, a stroke that results in only a limited degree of disability may be considered a mild stroke but would be a SAE when it satisfies the criteria shown in Appendix B2.

B7 A Guide to Interpreting the Causality Question

When making an assessment of causality consider the following factors when deciding if there is a ‘reasonable possibility’ that an AE may have been caused by the drug.

23. Time Course. Exposure to suspect drug. Has the patient actually received the suspect drug? Did the AE occur in a reasonable temporal relationship to the administration of the suspect drug?
24. Consistency with known drug profile. Was the AE consistent with the previous knowledge of the suspect drug (pharmacology and toxicology) or drugs of the same pharmacological class? Or could the AE be anticipated from its pharmacological properties?
25. De-challenge experience. Did the AE resolve or improve on stopping or reducing the dose of the suspect drug?
26. No alternative cause. The AE cannot be reasonably explained by another aetiology such as the underlying disease, other drugs, other host or environmental factors.
27. Re-challenge experience. Did the AE reoccur if the suspected drug was reintroduced after having been stopped? AstraZeneca would not normally recommend or support a re-challenge.
28. Laboratory tests. A specific laboratory investigation (if performed) has confirmed the relationship.

In difficult cases, other factors could be considered such as:

29. Is this a recognized feature of overdose of the drug?
30. Is there a known mechanism?

Causality of ‘related’ is made if following a review of the relevant data, there is evidence for a ‘reasonable possibility’ of a causal relationship for the individual case. The expression ‘reasonable possibility’ of a causal relationship is meant to convey, in general, that there are facts (evidence) or arguments to suggest a causal relationship.

The causality assessment is performed based on the available data including enough information to make an informed judgment. With limited or insufficient information in the case, it is likely that the event(s) will be assessed as ‘not related’.

Causal relationship in cases where the disease under study has deteriorated due to lack of effect should be classified as no reasonable possibility.

B8 Medication Error

For the purposes of this clinical study a medication error is an unintended failure or mistake in the treatment process for an AstraZeneca study drug that either causes harm to the participant or has the potential to cause harm to the participant.

A medication error is not lack of efficacy of the drug, but rather a human or process related failure while the drug is in control of the study site staff or participant.

Medication error includes situations where an error.

31. occurred
32. was identified and intercepted before the participant received the drug
33. did not occur, but circumstances were recognized that could have led to an error

Examples of events to be reported in clinical studies as medication errors:

34. Drug name confusion
35. Dispensing error e.g. medication prepared incorrectly, even if it was not actually given to the participant
36. Drug not administered as indicated, for example, wrong route or wrong site of administration
37. Drug not taken as indicated e.g. tablet dissolved in water when it should be taken as a solid tablet
38. Drug not stored as instructed e.g. kept in the fridge when it should be at room temperature
39. Wrong participant received the medication (excluding IVRS/IWRS errors)
40. Wrong drug administered to participant (excluding IVRS/IWRS errors)

Examples of events that **do not** require reporting as medication errors in clinical studies:

41. Errors related to or resulting from IVRS/IWRS - including those which lead to one of the above listed events that would otherwise have been a medication error
42. Participant accidentally missed drug dose(s) e.g. forgot to take medication
43. Accidental overdose (will be captured as an overdose)
44. Participant failed to return unused medication or empty packaging
45. Errors related to background and rescue medication, or standard of care medication in open label studies, even if an AZ product

Medication errors are not regarded as AEs but AEs may occur as a consequence of the medication error.

